### 6.3 Enhanced Data Collection Elements to Meet Secondary Objectives

For a more comprehensive list of data elements needed to meet the secondary objectives, see Appendix B.

- All inpatient/outpatient encounters for to-be-determined lead-in period (to refine high-risk conditions)
  - Medication prescribing/administration (e.g. asthma or immunosuppressive medications)
  - Laboratory testing/results (e.g. for diabetes, hemoglobin A1C tests)
- Respiratory syndrome-associated hospitalizations during influenza season of interest (all patients; discharge codes listed in Appendix D)

- Medication orders/administration (e.g. influenza antivirals, antibiotics, steroids, vasopressors)
- Expanded laboratory testing/results (e.g. CBC, CMP)
- Vital signs (e.g. heart rate, respiratory rate, blood pressure, temperature, O2 saturation, Glasgow Coma Scale)
- Non-invasive mechanical ventilation (e.g. CPAP, BiPAP, high flow nasal cannula)
- Radiography (e.g. chest x-ray)
- ARI syndrome-associated outpatient encounters during influenza season of interest (all patients; ICD codes TBD)
  - Medication orders/administration (e.g. influenza antivirals, antibiotics)
  - Expanded laboratory testing/results (e.g. CBC, CMP)
  - Vital signs (e.g. heart rate, respiratory rate, blood pressure, temperature, O2 saturation, Glasgow Coma)
  - Radiography (e.g. chest x-ray)

## **7.0 Data Sources and Management**

### **7.1 Data Sources**

Many of the required patient data variables are routinely captured in the EHR. Others may need to be added from additional sources such as participant health plan enrollment or administrative data, administrative claims, or vaccine registries linked to EHR data at the patient level. Reliance on open text fields, such as physician notes, will be kept to a minimum.

Each data element that is extracted will have an operational definition accounting for the coding structure, completeness, and limitations of the data source. This operational definition is particularly important to address situations that may arise when extracting data from health

records. For example, a concept (e.g. vaccination status) may be captured by more than one variable in a single provider database (e.g., recorded in vaccination records or in visit notes for self-reported) or in more than one database (e.g., EHR or vaccine registry). Thus the validity of the analyses will depend on consistent operational definitions.

Operational definitions for necessary data elements will be defined collaboratively by CDC, Westat, and network sites to ensure consistency and accuracy of definitions across sites. As the data coordinating center, Westat will receive data from the sites and derive variables for analysis. Alternatively, sites may choose to derive some or most data elements prior to submitting final datasets to Westat/CDC, based on the agreed-upon operational definitions. Appendix E displays an example of the types of data shared by the sites with Westat for processing.

At Westat, the study database will be housed in an integrated central research data warehouse (RDW) platform. The RDW will be fully integrated with the data management and tracking systems necessary for carrying out the processes associated with entry/upload, transmission, QA, version control, standardization, storage, and security.

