### **5.4 Exposures of Interest**

#### ***Vaccination status***

Within each annual retrospective cohort, an individual will be considered vaccinated for influenza if there is documented evidence of influenza vaccination and evidence that the vaccination was administered at least two weeks prior to an influenza-associated respiratory hospitalization (or influenza-associated ARI outpatient visit).

In order to assess influenza vaccination status, multiple sources will be queried, as available, including EHR, state/local vaccine registries, all-payer claims or other billing databases. For each available source, data will be provided on date of vaccination, type of vaccine administered, vaccination route, location of vaccination, vaccine lot number and number of vaccine doses (for children <9 years of age). Vaccination records will be considered as evidence of vaccination if there is at least a partial date (month and year). Children (aged <9 years) will be considered fully vaccinated for the current season if they received two doses, at least one month apart, during the current season or if they received one dose of the current season's vaccine and had at least two doses in prior seasons.

Network sites will provide information on number of sources queried for vaccine data and completeness of data by vaccine source. Because each site is querying multiple sources, a hierarchy of sources will be established for each site or through joint consensus with collaborating partners. For vaccination data extracted from EHRs, sites will provide information on how vaccination data was pulled (for example, through use of CPT or other codes).

For a subset of patients (number to be determined by joint consensus by the collaborating partners), accuracy of extracted vaccination data will be verified through manual review of source data (i.e. medical chart review).

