***Objective 2: Validation of influenza vaccination data***

- Describe the frequency of influenza vaccination among cohort members and vaccine type received. Descriptions will include the full cohort and will be stratified by individual characteristics such as age group, high-risk condition, and prior healthcare utilization.
  - Frequency of vaccination will be compared across strata using appropriate bivariate statistics (e.g. chi-square tests or Fisher's exact tests).
- Among those determined to be vaccinated for influenza
  - Assess the proportion that were identified through various data sources (e.g., procedure codes from a medical visit, other notation in the medical chart, vaccine registry, billing data, etc.). Assess whether the source of vaccination data varies by individual characteristics, including age group, high-risk conditions, and prior healthcare utilization.

- Compare the completeness and consistency of data on date of vaccination and vaccine type between data sources and by patient characteristics such as age group, high-risk conditions, and prior healthcare utilization.
- Comparisons of data by source, for completeness, and for consistency and how these differ by patient characteristics will be conducted using appropriate bivariate tests of association and/or multivariate regression. As an example, regression analyses could include data source as the outcome of interest with patient characteristics as explanatory variables.
- Describe the timing of vaccine receipt among cohort members by age group, high risk condition, prior healthcare utilization, and vaccine type received.

This description will be explored using a variety of methods, including time to vaccination, median week of vaccination, or frequency of vaccination at least two weeks prior to the start of influenza circulation. Comparison of timing by patient characteristics will be conducted using methods appropriate to the outcome type; for example, proportional hazards modeling for time to vaccination.

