***Objective 5: Assessment of vaccine effectiveness***

- We will estimate the effect of influenza vaccination on risk of lab-confirmed influenza-associated respiratory hospitalization by age group, influenza type/subtype, and high-risk conditions
  - The risk of influenza-associated respiratory hospitalization among cohort members who were or were not vaccinated with the current season influenza will be compared using appropriate methods for longitudinal data with time varying exposure, including Poisson regression or proportional hazards modeling.
  - VE will be estimated as  $(1 - \text{adjusted relative risk}) \times 100$ .
  - We will assess and adjust for confounders as appropriate. These may include characteristics such as age, sex, site, race/ethnicity, high-risk health conditions, prior healthcare utilization, time of event during the influenza season, etc.
  - Data collected for this study are intended to be pooled across sites. VE will first be estimated for each site and heterogeneity in estimated VE across sites examined.
- We will estimate the effect of influenza vaccination on risk of lab-confirmed influenza-associated ARI outpatient visit among children (adults only if influenza testing allows for this) by age group, influenza type/subtype, and high-risk conditions
  - The risk of influenza-associated outpatient visits among cohort members who were or were not vaccinated with the current season influenza will be compared using appropriate methods for longitudinal data with time varying exposure, including Poisson regression or proportional hazards modeling.
  - VE will be estimated as  $(1 - \text{adjusted relative risk}) \times 100$ .

- We will assess and adjust for confounders as appropriate. This may include characteristics such as age group, sex, site, race/ethnicity, high-risk health conditions, prior healthcare utilization, time of event during the influenza season, etc.
- Data collected for this study are intended to be pooled across sites. VE will first be estimated for each site and heterogeneity in estimated VE across sites examined.
- VE analyses against influenza-associated respiratory hospitalizations will also be conducted using a test-negative case-control design
  - This analysis will be conducted among individuals who were hospitalized for acute respiratory illness during the influenza season and who were tested for influenza.
  - Cases will be defined as hospitalized individuals who tested positive for influenza.

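### A dose first charted at the influenza encounter still counts as exposure, so cohort vaccine effectiveness is likely biased downward, by an unknown amount

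*Protocol*

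**What the plan says.** Protocol section 5.4 (Vaccination status) classes a member as vaccinated on documentation of a dose plus "evidence that the vaccination was administered at least two weeks prior to an influenza-associated respiratory hospitalization", or before the corresponding outpatient visit. A record carrying a month and year is enough. On sources it says that "multiple sources will be queried, as available, including EHR, state/local vaccine registries, all-payer claims or other billing databases". It sets no condition on when the record itself was made, and it leaves a hierarchy of sources to be agreed later.

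Section 6.1, Objective 2, gives examples of the sources through which members were determined to be vaccinated: "procedure codes from a medical visit, other notation in the medical chart, vaccine registry, billing data". It plans to compare source across age group, high-risk condition and prior utilization. Event status is not named.

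Section 7.1 mentions that vaccination may be "recorded in vaccination records or in visit notes for self-reported", as an example of what operational definitions must settle. It adds: "Reliance on open text fields, such as physician notes, will be kept to a minimum".

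Under Objective 5, risk "among cohort members who were or were not vaccinated with the current season influenza will be compared" with Poisson or proportional hazards models and time-varying exposure. Objective 4 calculates incidence separately for vaccinated and unvaccinated members. A test-negative analysis is planned for hospitalization only.

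**The concern.** Registry, claims and administered-dose records are pulled for every member and do not depend on the outcome. Chart notation can depend on it. If a member received a dose elsewhere that none of those sources holds, an influenza admission or acute respiratory illness (ARI) visit is an extra occasion on which it may be asked about and entered with a month and year. Because only the dose date is limited, that entry makes the case vaccinated retrospectively. A member with the same missing dose and no such encounter has one occasion fewer for it to be found.

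The effect is to move cases from the unvaccinated to the vaccinated numerator without moving the matching person-time. The vaccinated rate rises, the unvaccinated rate falls, and cohort VE falls. Adjustment for prior utilization does not remove this, because capture depends on the event itself. The hospitalization test-negative analysis is largely spared, since its cases and controls are all admitted. The two hospitalization estimates could therefore differ for this reason alone. Outpatient VE has no second estimate that would show it.

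The planned checks would probably miss it. Objective 2 does not name event status. Appendix G measures agreement with the primary record, and a dose never charted for an event-free member shows there as agreement.

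**Working it through.** **Plan's own figures.** The protocol gives no capture rate and no estimate of this bias, so there is no stated figure to reproduce. Table 1 (section 6.2) cannot be rebuilt either, because alpha, power and incidence are not stated. Section 6.2 does supply coverage:

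- Adults: 30%, 42% and 65% in equal thirds, so c = (0.30 + 0.42 + 0.65)/3 = 0.457.
- Children: 70% and 50% in equal halves, so c = 0.60.

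**Assumed inputs.** True VE is 40% (RR = 0.6). s0 is the share of true doses captured in the cohort's person-time, and s1 the share captured in members with the event. No unvaccinated member is recorded as vaccinated. Coverage is treated as constant over follow-up.

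**Formula.** Observed RR = (s1 × RR / s0) ÷ {[(1 − c) + (1 − s1) × c × RR] / (1 − s0 × c)}, and observed VE = 1 − observed RR.

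**Worked case, adults, s0 = 90%, s1 = 95%.**

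- First term: 0.95 × 0.6 / 0.90 = 0.6333.
- Second term: (0.5433 + 0.05 × 0.4567 × 0.6) / (1 − 0.90 × 0.4567) = 0.5570 / 0.5890 = 0.9457.
- Observed RR = 0.6333 / 0.9457 = 0.670, so VE = 33.0%.
- With equal capture (s1 = s0 = 90%): 0.6 / (0.5707 / 0.5890) = 0.619, so VE = 38.1%.
- Loss due to unequal capture: 38.1 − 33.0 = 5.1 points.

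**Adults, true VE 40%.**

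| s0 | s1 | Observed VE | VE if s1 = s0 | Loss (points) |
|---|---|---|---|---|
| 95% | 96.25% | 37.8% | 39.0% | 1.2 |
| 95% | 97.5% | 36.6% | 39.0% | 2.4 |
| 90% | 95% | 33.0% | 38.1% | 5.1 |
| 80% | 90% | 24.9% | 36.3% | 11.4 |

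In children (c = 0.60) at 90% against 95%, observed VE is 30.3% against 36.7% with equal capture, a loss of 6.4 points. For a vaccine with no effect, adults at 90% against 95% show a VE of −9.8%. Every case with s1 above s0 moves VE downward.

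**Scale.** Table 1 moves in 5-point steps of VE between 20% and 40%. The 90%/95% case is therefore worth about one row, and the 80%/90% case about two.

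**A cut-off for cases alone.** Suppose chart entries were dropped for cases from the encounter onward while event-free members kept theirs. With coverage 50%, true VE 40% and s0 = 80%, the vaccinated share of cases is 0.5 × 0.6 / (1 − 0.5 × 0.4) = 0.375, and the comparator odds are 0.4/0.6 = 0.667.

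- s1 = 75%: (0.28125/0.71875)/0.667 = 0.587, so VE = 41.3%.
- s1 = 70%: (0.2625/0.7375)/0.667 = 0.534, so VE = 46.6%.

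That rule can push VE above its true value, so it would not be a remedy.

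**The case against.** The case against has real force on four points.

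- **Section 7.1 is not an exposure rule.** A reader might infer from it that self-report in visit notes is an accepted source. The text offers it only as an example and says open text will be limited. The point rests on sections 5.4 and 6.1. The Objective 2 list is itself a set of examples, but it concerns members already determined to be vaccinated.
- **Event-free members are not without a chart.** It is tempting to say that they never have a vaccination history taken. Inclusion criteria 1 to 4 require care in the preceding 12 months, and section 5.4 expects encounters during and after the season, where outside doses can also be entered. The difference in capture is partial, and is confined to doses absent from the other sources.
- **The size is assumed.** At 50% coverage, capture of 80% against 95% would turn a true 40% into 17.0%, but that requires (95 − 80)/(100 − 80) = 75% of all missed doses to be found and dated at the outcome encounter. Nothing in the documents supports so wide a gap.
- **Some detail is deferred.** Source hierarchy and operational definitions are left to consensus, and the Appendix B codebook is a separate file that is not shown. It cannot be said that a record date is missing from the extract, only that section 5.4 does not list one among the vaccination fields.

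These points reduce the size and the certainty. They do not remove the mechanism: section 5.4 states the exposure definition and limits only the dose date, and none of the deferred items as described addresses record timing.

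**Conclusion.** The concern holds in a limited form. The exposure definition lets a dose first charted at the outcome encounter count, so capture is likely somewhat higher in members with the event, and cohort VE and the Objective 4 contrast are biased downward. The direction follows from the definitions provided capture is in fact higher in cases.

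The size is unknown. At the protocol's adult coverage and a true VE of 40%, it runs from about 1 to 2 points if chart-only doses are rare to about 11 points at 80% against 90% capture. A reader might infer that a large bias, or a spuriously negative VE, has been shown. It has not: those results depend wholly on capture rates the documents do not give. The change is worth making because the correction is simple and the planned checks would not reveal the problem.

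**What to change.** - **Exposure rule (section 5.4).** For the cohort analyses in Objectives 4 and 5, define vaccination for all members from sources filled independently of the outcome encounter: administered-dose records, registry, and claims or billing.
- **If historical or self-reported chart entries are used,** apply the same record-date rule to everyone. Either count person-time as vaccinated only from the date the entry existed, or use one common calendar cut-off, set before the analysed follow-up starts so that no event in it can trigger an entry. Do not apply a cut-off at the encounter to cases alone.
- **Check (Objective 2).** Add event status (respiratory hospitalization or ARI visit, yes or no) to the comparison of vaccination source.
- **Sensitivity analysis.** Report cohort VE using all records alongside the restricted definition.

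Cost: the source restriction needs a sentence in section 5.4 and a source variable that separates administered doses from other chart notation. Section 7.4 already expects a source wherever there is a vaccination date. A record-date rule costs more, because sites would need entry dates in data that may reach back to 2010/11. The statistical price is that some true doses are dropped, which gives modest attenuation toward the null: with equal capture of 80% to 95%, a true 40% in adults is seen as 36.3% to 39.0%.

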## **7.2 Variables**

A listing of the analytic variables necessary to meet the primary project objectives are shown in Appendix A. Depending on funding to address secondary objectives, additional variables will be added, including medications (antivirals, antibiotics, steroids, vasopressors), non-invasive mechanical ventilation, vital signs (such as heart rate, respiratory rate, blood pressure, temperature, O2 saturation, Glasgow Coma Scale), radiography, and other laboratory tests [including diabetes, hemoglobin A1C, complete blood count (CBC), comprehensive metabolic panel (CMP), etc.]. A listing of the analytic variables necessary to meet the primary

and secondary project objectives is provided in Appendix B. Additionally, Appendix D contains the ICD codes and other variables used to define high-risk conditions, ARI hospitalizations, and outcomes.

### **7.3 Data Management**

During the course of the study, research staff at each site will extract information from the EHR of participants, state or local vaccination registries, and billing records. Information for extraction includes data elements described in Section 7.2 and Appendices B and D. Sites will perform data validation on the extracted data as discussed in Section 7.4, below. Each site will create and maintain a database onsite that links demographic and clinical information extracted from the EHR, state or local vaccination registries, and billing records to a coded patient identifier. The key linking the coded identifier to the patient IDs will be kept at the individual sites. Additionally, the sites within a health network will also be given a coded identifier. Some details of the site will be included in the data, such as facility type (hospital, medical office, urgent care, ER, etc.), county, and state. Upon execution of an appropriate data use agreement (DUA) or data transfer agreement (DTA), a HIPAA-defined limited data set (LDS) will be forwarded (using a secured data transfer protocol) to the study coordinating center (Westat). Data transferred to Westat will not include identifying elements such as name, medical record number, postal address, or any other elements not allowed in a LDS. These datasets will contain individual-level records of pre-processed variables derived by the study site for the analysis necessary for the primary objectives.

Additional details about site data processing can be found in Appendix E, Proposed Data Structure to be shared by Sites with Westat. Westat will perform additional quality control and validation on the received data, as described in Section 7.4 below. Westat will derive the analytic

variables for sites sending data matching descriptions 1 and 2 above and concatenate the files to form one database. The database will be transferred to CDC using a secured transfer protocol for analysis (see Data Management Plan, Appendix F, for further detail).

#### **7.4 Data Validation**

Data will be validated at different points throughout the protocol and study period and will be an iterative process. If errors are found, Westat will coordinate with the site and the extraction will be re-programmed and data re-extracted and re-validated. Sites and Westat will both perform various aspects of this quality control and data validation. There are three main types of validation that will be conducted for this study:

1. Basic validation

The basic validation includes data quality checks such as confirmation that values are non-missing, values are of the correct type and length, and values are in the appropriate range. All variables will undergo basic validation. Expected variable type, length, and range will be included in the codebooks. Range checks will be particularly important for dates and healthcare utilization. Expected percent missing will be determined at the site-level. For example, some sites may do more influenza testing than others and thus the expected percent missing for those sites would be different.

2. Internal crosschecks

The internal crosscheck validation will include two types of checks. The first is comparing calculated proportions of various data elements in the extracted data to the proportions in the source data. For example, if a site generally performs influenza testing on 50% of its pediatric patients and the extracted data show only 5% that would indicate an error.

Variables that will undergo this check are sex, race, ethnicity, insurance coverage, insurance

type, respiratory virus testing and results (percent tested and percent positive), vaccination status (by age and high-risk condition), invasive mechanical ventilation, ICU admission, in-hospital mortality, and high-risk conditions.

The second type of internal crosscheck is comparing related data elements, i.e., a value for one data element is checked against the value for another data element. For example, all patients with a pregnancy-related diagnosis code should have sex recorded as female. Checks of this type could include:

- Number of inpatient visits corresponds to number of admission dates
- Number of outpatient visits corresponds to number of dates of outpatient encounters
- If date of vaccination is non-missing then source of data (EHR, registry, administrative records, etc.) should be non-missing
- If the date of respiratory virus testing is non-missing then the type of test and the test result should be non-missing; likewise, the test result should be consistent with what is detectable by the test type
- A patient with a record for mechanical ventilation should also have an ICU admission date

Additionally, sites could crosscheck the high-risk conditions with other data not extracted for this study. For example, they could look at medication use among those coded with high-risk conditions commonly treated with medication (e.g. asthma, diabetes).

